20.3 END OF TRIAL

The end of the trial will be defined as final database lock.

20.4 CONFIDENTIALITY

When consent forms are signed, a copy will be provided to the participant, a copy will be filed in the medical records and the original will be retained in the Investigator Site File. Participant initials and date of birth will be entered into the study database but no more identifying information will be collected outside of the recruiting study site.

When the study is complete, a data sharing dataset will be created from the raw data by the study analyst, which will not include participant initials, date of birth or any other identifiable data and study PIN will be altered so that individuals are not recognisable from the dataset.

The study will comply with the General Data Protection Regulations (GDPR)⁴⁹.

20.5 COVID-19 CONTINGENCIES

The recent COVID pandemic has impacted clinical trial work. BEACON trial visits should be conducted face to face. Safety visits for bloods/ blood pressure can be conducted in the community where appropriate and the week 30 safety assessment for those who switch to methotrexate or dupilumab after 6 months can be conducted remotely. If face to face review is not possible then month 1, 3 and 9 visits could be conducted remotely (after notification to the trial team/ manager) if supporting blood tests and blood pressure readings can be safely arranged locally but this is obviously not optimal for the completeness of data collection. Face to face review is essential for screening, baseline, month 6 and month 12.

20.6 FUNDING

This study is funded by the NIHR HTA Programme (NIHR 129926). The views expressed are those of the author(s) and not necessarily those of the NIHR or the Department of Health and Social Care. Additional specific funding is provided by Medac, who are supplying methotrexate (IMP) and funding to support methotrexate polyglutamate analysis, and Pfizer, who are providing funding for the addition of the fourth (abrocitinib) arm and supplying abrocitinib. Free of charge abrocitinib supply will end following full enrolment to and completion of the abrocitinib arm. Post-trial, participants on abrocitinib will be transitioned on to commercial supply with prescribing within licence and reimbursement as per national (NICE)/ local formulary requirements (see section 7.5 for information).

20.7 AVAILABILITY OF DATA AND MATERIALS

In those patients that give consent, data and materials will be stored on a on a secure NHS database and in the St. John's Research Tissue Bank (Ethics Committee ref: 07/H10712/106; HTA Licence number: 12521) respectively. De-identified data and materials (relating to patients who have specifically given consent) will be available for sharing upon request for future scientific research, subject to approval by the Chief Investigator and Programme Lead. This may involve data and study samples being transferred outside the UK and to commercial partners and/or vendors for the purposes of research.

20.8 INSURANCE AND INDEMNITY

This study is co-sponsored by Guys and St Thomas' NHS Foundation Trust (GSTFT) and King's College London (KCL). The co-sponsors will, at all times, maintain adequate insurance for the design, management and conduct of the study: (a) GSTFT through NHS Resolution cover, in respect of any claims arising as a result of negligence by its employees, brought by or on behalf of a study participant; and (b) KCL through its' own professional indemnity (Clinical Trials) & no fault compensation policy.

20.9 ARCHIVING

At the end of the trial, all trial data will be stored in line with the Medicines for Human Use (Clinical Trials) Amended Regulations 2006 and the 2018 Data Protection Act and archived in line with the Medicines for Human Use (Clinical Trials) Amended Regulations 2006 as defined in the KHP-CTO Archiving SOP. Recruiting sites will be responsible for archiving the source data, Investigator Site Files and Pharmacy Site Files.

APPENDIX 1 DRUG-SPECIFIC INFORMATION: CICLOSPORIN

TRIAL PARTICIPANT FLOW AND SCHEDULE OF EVENTS: CICLOSPORIN

	CICLOSPORIN SCHEDULE OF EVENTS												
Event / form	Screening	Baseline^	Week 2 Safety Visit	Week 4 (Month 1)	Week 6 Safety Visit	Week 8 Safety Visit	Week 13 (Month 3)	Week 15 Safety Visit ^B	Week 17 Safety Visit ^B	PRIMARY OUTCOME Week 26 (Month 6)	Week 39 (Month 9)	Week 52 (Month 12) End of Study Visit	Ongoing
Informed Consent	X												
Registration Form	X												
baseline)	X	Х											
Medical History and	v												
demographics	X												
Skin photography (optional)		Х								Х			
Randomisation Form (after all		х											
Status Form				Y			Y			Y	x	x	
Physical examination*	x	x		x			X			X	x	x	
Blood pressure	X	X								~			
Urinalysis	Х												
Pregnancy test*		Х											
Eczema Area and Severity Index (EASI) BLINDED ASSESSOR		x		х			x			x	x	x	
Investigator Global Assessment (vIGA-AD) BLINDED ASSESSOR		x		x			x			x	x	x	
Patient Orientated Eczema Measure (POEM)		х		Х			х			х	Х	х	
Peak pruritus numerical		х		Х			х			х	Х	х	
Eczema control (RECAP)		х		х			х			х	x	x	
Patient global assessment (PtGA)		x		X			X			X	x	x	
Dermatology Life Quality Index (DLQI)		х		х			Х			х	х	х	
EQ-5D-5L		Х					Х			Х	Х	Х	
PHQ-9		X								X		X	
GAD-7		X					v			X	v	X	
Adherence check (VAS) &		^					^			^	^	^	
Tolerability							Х			Х	Х	X	
Participant Online Surveys		Х										Х	
Dispense medication		Х					Х			Х	Х		
Screening blood tests (+DNA for filaggrin status, optional)	x												
Safety Blood Tests (can be remote)		х	х	X	X	х	Х	х	х	х	X	x	
Sarety Blood Pressure (can			Х	Х	Х	Х	Х	Х	Х	Х	X	X	
Safety urinalvsis				Х	1		х			Х	х	X	
Study medication switch		1		-	1			1	1	v		1	
review										^			
Study medication dose increment review							Х				X		
Concomitant Medications Log		v		v	 		Y			v			X
Adverse Events Log				X			X			*		 	Y
Withdrawal Form			 		1							 	X
* Physical examination (according to	o routi	ne clini	ical ca	re) requir	ed at	scree	ening a	and ba	seline,	extent of	physical	exam du	iring
follow up as deemed appropriate by investigator													
* Women of childbearing potential only. Urine test													

A: Baseline safety bloods for all treatments, at investigator discretion based upon timing of screening bloods

B: Week 15 & 17 safety bloods and safety blood pressure check if ciclosporin dose increased at week 13

Please note: if IMP is switched at 6 months, the schedule of events for the second IMP must be followed for the second 6 months of the trial.
CONTENTS

1	CICLO	SPORIN-SPECIFIC INFORMATION	74
	1.1	BACKGROUND	74
	1.1.1	Background and mechanism	74
	1.1.2	Rationale for use of ciclosporin	74
	1.1.3	Ciclosporin dose justification	74
	1.1.4	Rationale for 6 month switch option from ciclosporin (dupilumab)	
	1.2	CICLOSPORIN TOXICITY AND SAFETY	74
	1.2.1	Common side effects	
	1.2	2.1.1 Renal impairment	75
	1.2.2	Uncommon side effects	
	1.2.3	Rare side effects	
	1.2.4	Drug interactions	75
	1.3	SELECTION OF PARTICIPANTS	75
	1.3.1	Participant core inclusion and exclusion criteria	75
	1.3.2	Ciclosporin-specific exclusion criteria	75
	1.4	TREATMENT AND MONITORING OF PARTICIPANTS	75
	1.4.1	Product information	75
	1.4.2	Safety visits and monitoring requirements	76
	1.4	2.1 Safety visits (additional to main trial visits)	76
	1.4	.2.2 Safety blood pressure readings	76
	1.4	-2.3 Safety Diodas	//
	1/4 1/2	Managing toxicity with ciclosporin	
	1.4.5 1 1 1 1	Fugluating AF's and SAF's – assessment of expectedness	
	15	Recedences	
	1.5	NEI ENENCES	

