Dermatology Life Quality Index (DLQI)		х		х			х			х			х			х	
EQ-5D-5L		Х					Х			Х			Х			Х	
PHQ-9		X								X						X	
GAD-7		X					v			X			v			X	
Adherence check (VAS) &							х			x			x			X	
I olerability		v														v	
Dispense medication		Ŷ					Y			Y			Y			^	
Screening blood tests (+DNA			 				Λ										
for filaggrin status, optional)	X				 												
remote)		Х	х	X+++	Х	X	X	Х	Х	X	Х	Х	X++++	X	Х	Х	
be remote)**			Х	X	Х	X	X	Х	Х	X			X			X	
Safety urinalysis**				X			X			X			X			X	
Safety assessment (can be remote)***												Х					
Methotrexate polyglutamate sample****				х			х			х							
Study medication switch review										X							
Study medication dose							х						х				
Concomitant Mediactions Las							-						-				v
Topical treatments		x		X			x			x							^
Adverse Events Loa		~	 				~										Х
Withdrawal Form			1														Х

The electronic version of this document is the latest version. It is responsibility of the individual to ensure any paper material is the current version. Printed material is uncontrolled documentation. BEACON_PROTOCOL_VERSION 2.1_29/01/2025 Page 26 of 110

BEACON

* Physical examination (according to routine clinical care) required at screening and baseline, extent of physical exam during follow up as deemed appropriate by investigator

** Only required for those on ciclosporin

*** Only for those who switched treatment at 6 months

- ****Only required for those on methotrexate
- + Women of childbearing potential only. Urine test

** Repeat pregnancy test at 6 months for patients changing treatment from dupilumab or abrocitinib to methotrexate

*** Not required for those on dupilumab from the start (week 39 blood tests required for those who switch to dupilumab)

++++ Not required for those on dupilumab or abrocitinib from the start (week 39 blood tests required for those who switch to dupilumab)

A: Baseline safety bloods for all treatments, at investigator discretion based upon timing of screening bloods. Baseline safety blood pressure check if randomised to ciclosporin only.

B: Week 2 Safety bloods and safety blood pressure check if randomised to ciclosporin, week 2 safety bloods if randomised to methotrexate

C: Week 6 & 8 Safety bloods and safety blood pressure check if randomised to ciclosporin only

D: Week 15 & 17 Safety bloods and safety blood pressure check if dose increased on ciclosporin, week 15 & 17 safety bloods if dose increased on methotrexate

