6.5.2 BLOOD PRESSURE

Blood pressure will be measured at screening and baseline. The need for any drug-specific additional safety assessment blood pressure readings is stated in the individual drug appendices
(Appendices 1-4). Blood pressure should be measured in an upright position after the participant has been rested for five minutes

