1.4.2.1 SAFETY VISITS (ADDITIONAL TO MAIN TRIAL VISITS)

All participants randomised to ciclosporin will be followed up for safety at week 2 with additional visits at weeks 6 and 8. In addition, if their dose is increased at 3 months, they will be seen at weeks 15 and 17. In the event of dose reduction, additional safety assessments should be arranged at the discretion of the investigator.

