1.4.2.2 SAFETY BLOOD PRESSURE READINGS

Safety assessment blood pressure readings will be measured at weeks 2, 4, 6, 8, 12, 24, 39 and 52 for those on ciclosporin. For those who dose increment on ciclosporin at month 3 additional blood pressure measurements will be taken at weeks 15 and 17 (see schedule of events, main protocol Section 2). Blood pressure should be measured in an upright position after the participant has been rested for five minutes

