1.4.2.3 SAFETY BLOODS

The following safety bloods will be performed at weeks 2, 4, 6, 8, 13, 26, 39 and 52. For those who dose increment on ciclosporin at month 3 additional safety bloods will be performed at weeks 15 and 17 (see schedule of events, main protocol Section 2).

HAEMATOLOGY Haemoglobin Haematocrit Total and differential leukocyte count Red blood cell count Platelet count BIOCHEMISTRY Creatinine Potassium Liver function tests (LFTs) *Lipids *Urate

*screening and at months 3, 6, 9 and 12 only

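### Extra ciclosporin bloods and blood pressure are scheduled only after a month-3 dose increase, so a later increase may wait up to 13 weeks for a scheduled check (minor safety point)

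*Protocol*

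**What the plan says.** Footnote B of the ciclosporin schedule of events in Appendix 1 reads: "Week 15 & 17 safety bloods and safety blood pressure check if ciclosporin dose increased at week 13". The appendix text repeats the same trigger three times:

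- Section 1.4.2.1, visits: "if their dose is increased at 3 months, they will be seen at weeks 15 and 17".
- Section 1.4.2.2, blood pressure: "For those who dose increment on ciclosporin at month 3 additional blood pressure measurements will be taken at weeks 15 and 17".
- Section 1.4.2.3, bloods: "For those who dose increment on ciclosporin at month 3 additional safety bloods will be performed at weeks 15 and 17".

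Table 1 footnote D in section 2 names the same two weeks: "Week 15 & 17 Safety bloods and safety blood pressure check if dose increased on ciclosporin".

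The row "Study medication dose increment review" in the ciclosporin schedule carries marks at week 13 and at week 39. Section 1.4.1 of Appendix 1 allows the step from 3 to 5 mg/kg once three months have passed and does not confine it to the week-13 visit. Section 7.2 of the main protocol encourages sites to follow the suggested increases for ciclosporin and methotrexate, but permits other dose changes where there is a clinical reason.

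Section 1.4.2.1 has a clause for dose changes at other times, but only for reductions: "In the event of dose reduction, additional safety assessments should be arranged at the discretion of the investigator".

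**The concern.** The protocol asks for bloods and blood pressure soon after a ciclosporin increase because the dose has gone up. That reason does not depend on when the increase is made, but the provision is written for month 3 only. A site that follows the printed schedule and raises the dose later finds no visit to book.

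What is at stake is participant safety. Appendix 1 section 1.2.1.1 describes impaired kidney function on ciclosporin as common, possibly serious, related to dose and reversible at first. Section 1.2.1 lists hypertension among the common side effects. A change that reverses on dose reduction is worth finding early. The discretionary clause covers the direction of lower risk (reduction) and omits the direction of higher risk (increase).

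**Working it through.** No sample size, power or error-rate figure is involved. The check compares the schedule with itself.

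**Inputs**

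- Increment-review marks, ciclosporin schedule (Appendix 1): weeks 13 and 39.
- Routine ciclosporin bloods (Appendix 1, 1.4.2.3): weeks 2, 4, 6, 8, 13, 26, 39, 52.
- Routine blood pressure (1.4.2.2): the text gives weeks 12 and 24 where the schedule has 13 and 26. Both have weeks 39 and 52, so the late interval is the same.
- Extra checks after an increase: weeks 15 and 17, for a month-3 increase.
- Week 41 and 43 bloods (Table 1 footnote G): only participants who switched to methotrexate and had their dose raised.
- Visit window (section 6.1.1): 7 days either side.
- Planned dose step: 3 to 5 mg/kg.

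**Gap to the next scheduled check** = week of next scheduled check − week of increase.

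- Week-13 increase: 15 − 13 = 2 weeks, then 17 − 13 = 4 weeks. Two extra checks within 4 weeks.
- Week-39 increase: 52 − 39 = 13 weeks. No check within 4 weeks. With the visit windows the interval runs from 51 − 40 = 11 to 53 − 38 = 15 weeks.
- Off-schedule examples: week 20, 26 − 20 = 6 weeks; week 30, 39 − 30 = 9 weeks; week 40, 52 − 40 = 12 weeks.
- Early off-schedule example: week 4, 6 − 4 = 2 and 8 − 4 = 4 weeks. The routine early visits cover this case by chance, so the gap matters mainly after week 13.

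Routine checks from week 13 on are 13 weeks apart (26 − 13, 39 − 26, 52 − 39), so 13 weeks is the longest nominal wait. An increase shortly before a routine visit gets one early check but not a second within 4 weeks.

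**Size of the planned step:** 5 / 3 = 1.67, an increase of 67%.

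**Is a week-39 ciclosporin increase intended?** Probably not.

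- The synopsis and section 2 place the optional increase at 3 months.
- Section 2 raises a month-9 increase only for participants who have switched drug. Section 1.1.4 of the four appendices sends ciclosporin and methotrexate non-responders to dupilumab, and dupilumab and abrocitinib non-responders to methotrexate. Nobody switches to ciclosporin.
- The dupilumab and abrocitinib schedules carry the same row with the same marks, although neither drug has a planned increase.

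The mark therefore looks like a template carry-over. The gap does not depend on it, because section 7.2 and the dose rule in 1.4.1 still allow a later increase.

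**After the fix:** a week-39 increase would be checked at weeks 41 and 43, so the first gap falls from 13 weeks to 2.

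**The case against.** The strongest reply is that the likely defect is one stray mark, and that the 13-week figure assumes a site acts on it. No fixed calendar can list visits for unplanned dose changes. Section 7.2 requires a clinical reason, section 6.7 allows unscheduled laboratory tests when the investigator judges them necessary, and Appendix 1 section 1.4.3 links national prescribing guidance and refers to the product information for toxicity. In a pragmatic trial close to routine care, a competent clinician would check creatinine and blood pressure after raising ciclosporin. Section 2 also sends the reader to Figure 2 and the drug flow diagrams, which are not shown here and may say whom the month-9 review covers.

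Much of this stands. A reader might infer that the protocol plans a month-9 ciclosporin increase and leaves it unmonitored, or that monitoring after a late increase is absent or barred. The documents support neither: the mark is probably unintended, and discretion remains.

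Discretion does not close the gap, however. The section 6.7 clause names laboratory tests only. For blood pressure, section 6.5.2 says "The need for any drug-specific additional safety assessment blood pressure readings is stated in the individual drug appendices", and Appendix 1 provides extra readings only after a month-3 increase. The reference to product information applies once toxicity has appeared, whereas scheduled checks are there to find it. A calendar cannot list unplanned visits, but a rule counted from the date of the increase can.

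**Conclusion.** The point holds as a minor participant-safety improvement. As printed, a ciclosporin increase after month 3 may have no scheduled bloods or blood pressure for up to 13 weeks (week 39 to week 52), against the 2 and 4 weeks that the protocol requires after a week-13 increase.

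The 13 weeks is nominal and assumes that an increase is actually made at week 39; other off-schedule times give shorter waits. The protocol offers no basis for counting affected participants. The number is probably small: only month-6 responders who tolerate ciclosporin stay on it, and those already at 5 mg/kg have no planned step left. A reader might also infer a threat to the trial's main result. A week-39 increase comes after the 6-month assessment, and the gap concerns the timing of safety checks, so the primary outcome is not affected.

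The verdict rests on the text and tables. The flow diagrams may explain the week-39 mark, but the appendix wording would still not cover the off-schedule increases that section 7.2 permits.

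**What to change.** Two changes at the next amendment:

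1. Reword footnote B, Appendix 1 sections 1.4.2.1 to 1.4.2.3 and Table 1 footnote D so that bloods and blood pressure are required 2 and 4 weeks after any investigator-prescribed increase in the daily ciclosporin dose above the participant's previous highest tolerated dose, whenever it is made. A scheduled visit falling at that point counts. This trigger leaves out weight loss on an unchanged dose and a return to a dose already tolerated.
2. If no month-9 ciclosporin increase is intended, delete the week-39 mark from the increment-review row. This alone would not be enough, because it leaves off-schedule increases uncovered.

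The cost is wording, similar in kind to the version 2.1 correction of the abrocitinib week-4 bloods. The added burden is at most two conditional checks per increase, and section 2 allows safety-only visits to be done in the community. A week-13 increase keeps its week-15 and week-17 checks unchanged.

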1 CICLOSPORIN-SPECIFIC INFORMATION

1.1 BACKGROUND

1.1.1 BACKGROUND AND MECHANISM

Ciclosporin is a highly effective and rapidly acting potent inhibitor of T-cell function. Ciclosporin is a prodrug that forms a complex with the intracytoplasmic protein cyclophilin. This complex inhibits calcineurin phosphatase, an enzyme which normally facilitates dephosphorylation of NF-ATc and subsequent transcription of pro-inflammatory cytokines including IL-2, IL-4, IFN- γ , transforming growth factor- β and up-regulation of receptors such as IL-2R (CD25). Ciclosporin thereby inhibits T-cell function (IL-2 and IL-2R are key regulators of T-cell activation) and additionally reduces histamine release and down-regulates high-affinity immunoglobulin E (IgE) receptors on mast cells and basophils¹.

1.1.2 RATIONALE FOR USE OF CICLOSPORIN

Ciclosporin is the control in this trial because of its strong evidence base (see section 1.1.1 and 1.4 in main protocol for further background information) and as the only licensed 'standard' systemic treatment for treating atopic eczema.

1.1.3 CICLOSPORIN DOSE JUSTIFICATION

Ciclosporin will be initiated at 3mg/kg and increased to 5mg/kg when required, consistent with dose ranges in previous RCTs^{2,3}, SmPC, national guidance, and a UK wide clinician survey that we carried out via the UK Dermatology Clinical Trials Network (UK DCTN, dosing schedule preferred by > 50%, all respondents happy to use this regimen). In psoriasis (where there is better evidence for using ciclosporin), an RCT and a meta-analysis suggested that doses of > 5mg/kg increase the risk of adverse events (AEs) but with little increase in efficacy, < 2.5mg/kg have low rates of AEs but a significant drop in efficacy, and 3 mg/kg or less were less likely to be associated with AEs than doses >5 mg/kg⁴. These data support a 3mg/kg starting dose, to optimise effect and minimise risk. As there is no data to suggest that 4mg/kg is less likely to result in AEs than 5mg/kg, and in line with clinical practice (>80% clinicians surveyed reported using 5mg/kg as their maximum dose, preferred dosing schedule 3 to 5mg/kg), a 5mg/kg higher dose was chosen to optimise effect.

1.1.4 RATIONALE FOR 6 MONTH SWITCH OPTION FROM CICLOSPORIN (DUPILUMAB)

For those participants on ciclosporin who do not meet response criteria to continue at 6 months they can switch to dupilumab. Dupilumab was chosen as the switch option to most closely mirror clinical practice (in line with NICE TA534).

1.2 CICLOSPORIN TOXICITY AND SAFETY

Administration of ciclosporin for this study is not anticipated to induce any potential risk other than the known potential side effects listed below (please refer to the SmPC of the branded drug dispensed).

1.2.1 COMMON SIDE EFFECTS

Diarrhoea; electrolyte imbalance; fatigue; fever; flushing; gastrointestinal discomfort; gingival hyperplasia; hair changes; headaches; hepatic disorders; hyperglycaemia; hyperlipidaemia; hypertension; hyperuricaemia; leucopenia; muscle complaints; nausea; paraesthesia; peptic ulcer;

renal impairment (renal structural changes on long-term administration); seizure; skin reactions; tremor; vomiting.

1.2.1.1 RENAL IMPAIRMENT

Renal impariment is a frequent and potentially serious complication that can occur during ciclosporin therapy. These functional changes are dose-dependent and are initially reversible, usually responding to dose reduction. During long-term treatment, some patients may develop structural changes in the kidney (e.g. interstitial fibrosis).

